### (2) PK related

The analysis visit window will be the following.

For Part 1 and 2

Analysis visit	Nominal time(hour)	Window
Pre dose	0	-60 min to 0
Day 1 0.5H – 1.5H	0.5 - 1.5	within $\pm$ 5 min
Day 1 2H – 3H	2 - 3	within $\pm$ 15 min
Day 1 4H - 6H	4 - 6	within $\pm$ 30 min
Day 1 8H - 16H	8 - 16	within $\pm$ 3 hour
Day 2	24	within $\pm$ 3 hours
Day 3	48	within $\pm$ 6 hours
Day 4	72	within $\pm$ 12 hours
Day 6	120	within $\pm$ 18 hours
Day 9 - Follow up	192 - 336	within $\pm$ 24 hours

For Part 3 except for urine PK

Analysis visit	Nominal time(hour)	Window
Pre dose	0	-60 min to 0
Day 1 0.5H – 1.5H	0.5 - 1.5	within $\pm$ 5 min
Day 1 2H – 3H	2 - 3	within $\pm$ 15 min
Day 1 4H – 6H	4 - 6	within $\pm$ 30 min
Day 1 8H – 16H	8 - 16	within $\pm$ 1 hour
Day 2 to LDD-1		within $\pm$ 3 hour
LDD 0.5H – 1.5H	0.5 - 1.5	within $\pm$ 5 min
LDD 2H – 3H	2 - 3	within $\pm$ 15 min
LDD 4H – 6H	4 - 6	within $\pm$ 30 min
LDD 8H – 16H	8 - 16	within $\pm$ 1 hours
LDD +1		within $\pm$ 6 hours
LDD +2		within $\pm$ 6 hours
5 days after last dose		within $\pm$ 12 hours
8 days after last dose		within $\pm$ 24 hours
Follow up	Day 15	within $\pm$ 24 hours

The analysis visit window for Urine PK is within the following time after the nominal time;  
-30 to +30 minutes.

### 7.3 Data Handling Convention for Missing Data

#### (1) Non-PK related

Adverse events:

If severity or relationship is found to be missing, the most severe occurrence will be imputed for the summary of interest.

For missing or partial AE start dates, the AE will be treated as a TEAE if it cannot be determined to be a non-TEAE. Adverse events with unknown start and/or end times (but where the date is known) will be imputed with a time of 23.59 h for the tabulations but will be shown as NK:NK in the listings (where NK = Not Known)

Other Safety-related endpoints:

For other safety-related summaries, only observed data will be used. Unless otherwise specified, missing safety data will not be imputed.

#### (2) PK related

For PK summaries, only observed data will be used. Missing PK data will not be imputed.

When calculating Ae and Ae%, missing PK data will be imputed to 0.

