8. Continuous ECG will be collected from approximately 24 hours prior to dosing on Day -1 until pre-dosing on Day 1; and from pre-dose on the LDD to 24 hours after last dosing (LDD +1). ECG extractions to occur at each PK blood sampling time point during this period.
9. A 12-lead ECG (heart rate and cardiac intervals: PR, QRS, QT and QTcF) will be performed at Day -1 (-0.5, 1, 2, 3 and 8 hours relative to expected dose time on Day 1); Days 1, 8 and LDD (at pre-dose, 1, 2, 3 and 8 hours post-dose); Days 2 to 7 (pre-dose); Days 9 to the day before the LDD (pre-dose); and 24 hours and 72 hours after the LDD (LDD +1 and LDD +3).
10. If dosing is extended beyond 14 days, a blood sample will be taken on Day 14 and every 7 days thereafter.
11. PK blood samples for MT-6345 will be collected on Day 1 (pre-dose and at 0.5, 1, 1.5, 2, 3, 4, 5, 6, 8, 12 and 16 hours post-dose), Day 2 to LDD -1 (pre-dose), LDD (pre-dose and at 0.5, 1, 1.5, 2, 3, 4, 5, 6, 8, 12 and 16 hours post-dose), and on LDD +1 (24 hours post last dose), LDD +2 (48 hours post last dose) and LDD +3 (72 hours post last dose).
12. [REDACTED]
13. PK urine samples for MT-6345 will be collected at Day -1 (-24 hours 0 hours), Day 1 (0 hours to 24 hours) and LDD (0 hours to 24 hours).
14. [REDACTED]

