**Last day of dosing (Day 14 or extended up to maximum Day 28)**

- Body weight and BMI.
- Vital signs (pre-dose; including supine blood pressure, pulse rate, respiratory rate and oral body temperature).
- 12-lead ECG (at pre-dose, 1, 2, 3 and 8 hours post-dose).
- Continuous ECG recorded from pre-dose to 24 hours post last dose (last day of dosing +1).
- [REDACTED]
- PK blood sampling for MT-6345 at pre-dose and 0.5, 1, 1.5, 2, 3, 4, 5, 6, 8, 12 and 16 hours post-dose.
- [REDACTED]
- PK urine sampling for MT-6345 at 0 hours to 24 hours post-dose.
- [REDACTED]
- AE and concomitant medication recording.

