**6.4.2 Collection of urine samples for pharmacokinetic analysis of MT-6345 and [REDACTED]**

Subjects will be required to empty their bladders approximately 30 minutes prior to dosing and immediately after blood sampling at the end of each collection period. The actual date, time and volume of each urine collection period will be recorded in the source documents and eCRF.

For each PK assessment, two urine samples will be taken from the volume of urine collected (one as a primary sample and one as a contingency sample).

Pharmacokinetic and [REDACTED] will be sent by courier from [REDACTED] [REDACTED] to [REDACTED] and [REDACTED], MTPC. Contingency samples will be shipped separately to the primary samples.

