## 2.2.2. Secondary Endpoints

### Pharmacokinetic assessments:

Plasma concentration versus time profile of MT-6345 after single and multiple dosing.

The following PK parameters will be calculated for MT-6345 after single dosing:

- Maximum plasma concentration after administration ( $C_{max}$ )
- Time to maximum plasma concentration ( $t_{max}$ ).
- Plasma terminal elimination half-life- ( $t_{1/2}$ ).
- Area under the plasma concentration-time- curve from time zero to 24 hours ( $AUC_{0-24h}$ ).
- Area under the plasma concentration-time- curve from time zero to the last measurable concentration ( $AUC_{0-last}$ ).
- Area under the plasma concentration-time curve from zero up to infinity with extrapolation of the terminal phase ( $AUC_{0-\infty}$ )
- Terminal elimination rate constant (Kel).
- Mean residence time (MRT).
- Apparent oral clearance (CL/F).
- Apparent volume of distribution during terminal phase ( $Vz/F$ )
- Apparent volume of distribution at steady state ( $Vss/F$ )

The following PK parameters will be calculated for MT-6345 after multiple dosing where appropriate:

- $C_{max}$ .
- $t_{max}$ .
- $t_{1/2}$ .
- Area under the plasma concentration-time- curve over the dosing interval ( $AUC_{0-\tau}$ ).
- $AUC_{0-last}$ .
- $AUC_{0-\infty}$ .
- Kel.
- MRT.
- CL/F.

- Apparent volume of distribution at steady state ( $V_{ss}/F$ ).
- Apparent volume of distribution during terminal phase ( $V_z/F$ )
- Linearity factor (LF).
- Accumulation ratio (AR).
- Urinary excreted amount of test compound (Ae).
- Urinary excreted amount of test compound expressed as a percentage of the dose administered (Ae%).
- Renal clearance ( $CL_R$ ).

QT interval assessments

Continuous 12-lead Holter data will be obtained from subjects in Parts 1 and 3. Data will be analysed following completion of the study to investigate the potential effect of MT-6345 on QTc interval or stored for future analysis.

2.2.3. [REDACTED]

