### 7.1.3.2. Pharmacokinetic Parameters

For the calculation of PK parameters, actual sampling time (in hours rounded to 2 decimal places) relative to dosing should be used. Concentration below the limit of quantification (BLQ) will be imputed with a value of 0. For calculation of AUCs, missing data will be treated as if the respective sample never had been scheduled for the calculation by the linear-linear trapezoidal rule.

For Ae, Ae% and CLR, geometric mean and geometric CV% will be calculated only when all the individual Ae, Ae% and CLR is greater than 0 at each sampling time point.

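### SAP 7.3(2) sets missing urine data to 0 for Ae and Ae%, so one missing 0-24 h result becomes a false zero and removes that day's geometric summary

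*SAP*

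**What the plan says.** SAP 7.3(2) gives two rules in succession. The general one is: "For PK summaries, only observed data will be used. Missing PK data will not be imputed". The exception follows directly: "When calculating Ae and Ae%, missing PK data will be imputed to 0". Nothing limits the exception to part of a collection or to a particular kind of missing result.

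SAP 7.1.3.2 already deals with results below quantification: "Concentration below the limit of quantification (BLQ) will be imputed with a value of 0". Appendix 1 repeats this. The same section restricts the urine summaries: "geometric mean and geometric CV% will be calculated only when all the individual Ae, Ae% and CLR is greater than 0", applied at each sampling time point.

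The urine schedule is in Protocol Table 4, footnote 13: "PK urine samples for MT-6345 will be collected at Day -1 (-24 hours 0 hours), Day 1 (0 hours to 24 hours"), plus the last day of dosing. Protocol 5.2.2.2 says the same for that last day: "PK urine sampling for MT-6345 at 0 hours to 24 hours post-dose". The matching footnote to SAP Table 3 agrees.

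SAP 6.1(2) and 8.3.2 plan arithmetic and geometric summaries of the urine parameters by dose level.

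**The concern.** A missing result and a zero result mean different things. If urine was not collected in full, or its volume or concentration is lost, the amount excreted is unknown. Entering 0 asserts that nothing was excreted.

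When Ae is summed over several intervals, a zero for one gap only understates the total. Here each profile day has one post-dose interval, so the zero replaces the whole value.

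The false value would pull down the mean, median and minimum, inflate SD and CV%, and remove the geometric summary for that dose level and day. Renal clearance would also be affected if it is derived from Ae, but Appendix 1 gives no formula for it.

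The rule also departs from the SAP's handling elsewhere. For AUC, a missing plasma sample is treated as never scheduled (7.1.3.2). A trough ratio with a BLQ numerator or denominator is shown as not calculated and left out of the summary (7.1.4).

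**Working it through.** The plan states no figure on this point, so there is none to reproduce. The check traces the rule and then sizes one imputed zero.

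**Tracing the rule**

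1. BLQ concentrations are already 0 under SAP 7.1.3.2 and Appendix 1. The 7.3(2) sentence therefore adds something only where a volume or concentration is absent.
2. There is one post-dose interval, 0-24 h, on each of Day 1 and the last dosing day. No other interval contributes to that day's Ae.
3. Ae for the day is then 0, and so is Ae%.
4. One zero fails the condition that all individual values exceed 0, so the geometric mean and geometric CV% are not calculated for that dose level and day.

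**Inputs for the size**

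- Part 3 enrolled 8 subjects (SAP 3.3.2). The active/placebo split is not stated.
- At most 3 placebo subjects were planned per cohort (SAP 3.1.1), so active n is 8 − 3 = 5 up to 8 − 0 = 8. The 3:1 ratio in SAP 3.3.1 would give 6.
- The true CV (20%, 30%, 50%) and the missing rate per collection (1% to 5%) are assumptions, because the documents give neither.

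**Formulas, one zero among n active subjects**

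- Mean with the zero ÷ observed mean = (n − 1)/n, a fall of 1/n.
- CV with the zero = √[ ((n − 2)/(n − 1))·cv² + 1/n ] ÷ ((n − 1)/n), where cv is the CV of the n − 1 observed values.

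Example, n = 5 and cv = 0.30: √(0.75 × 0.09 + 0.20) ÷ 0.80 = √0.2675 ÷ 0.80 = 0.647.

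| Active n | Fall in mean | CV from 20% | CV from 30% | CV from 50% |
|---|---|---|---|---|
| 5 | 20.0% | 59.9% | 64.7% | 77.8% |
| 6 | 16.7% | 53.5% | 58.6% | 72.7% |
| 7 | 14.3% | 49.0% | 54.5% | 69.1% |
| 8 | 12.5% | 45.6% | 51.4% | 66.6% |

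**Chance of at least one missing result on a given day** = 1 − (1 − p)ⁿ

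- n = 5: 1 − 0.99⁵ = 4.9%; 1 − 0.95⁵ = 22.6%.
- n = 8: 1 − 0.99⁸ = 7.7%; 1 − 0.95⁸ = 33.7%.

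**With the value left missing**, the mean is that of the n − 1 observed values, and the geometric statistics can be calculated if those are all above 0.

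**The case against.** **Discretion.** SAP 2.2.2 introduces the list containing Ae, Ae% and CLR with "The following PK parameters will be calculated for MT-6345 after multiple dosing where appropriate", and Protocol 10.3.5.2 qualifies their summaries in the same way. A pharmacokineticist could use this to decline to compute Ae. That is a real mitigation. However, it does not override an explicit instruction to enter 0, and SAP 8.3.2 plans the urine summary without the qualifier. The evaluability condition in SAP 5 and the data handling document in SAP 7.4 do not mention missing urine either.

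**Another intent.** The sentence may be standard text for summing over intervals; Protocol 10.3.5.2 does speak of each collection interval. That may explain its origin, but it does not fit a schedule with one post-dose interval per profile day.

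**Back-up sample.** Protocol 6.4.2 says: "For each PK assessment, two urine samples will be taken from the volume of urine collected", one of them for contingency. This can rescue a lost concentration, but not a missing volume or a failed collection.

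**The rule may never have operated.** This is the strongest point, and it stands as a limit.

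- The study was terminated, and assessments not performed are grayed out in a way this copy does not show.
- The Part 3 non-PK reporting visits in SAP 9.3 stop at Day 3 plus Day 15 follow-up, so there may have been only one post-dose collection day.
- The PK analysis set requires study completion, which could leave no Part 3 urine summary.
- SAP 10 does not list urine PK as dropped, but that settles little. It also omits Part 3 dose proportionality, although with a single enrolled dose cohort that slope could not be estimated anyway.

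**Range.** Eight active subjects would mean no placebo in Part 3, which sits badly with the placebo column in SAP 9.2. That row is the mild end of the range, and the conclusion does not depend on it.

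**Conclusion.** The concern holds: as written, the rule turns a missing 0-24 h urine result into a false Ae and Ae% of 0. One such result lowers the arithmetic mean by 12.5% to 20% (16.7% with 6 active), roughly doubles an assumed CV of 30%, and removes the geometric summary for that dose level and day.

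The importance is minor. Ae, Ae% and CLR are descriptive; no test, primary endpoint or escalation rule uses them, and a zero would show in the listing. The effect arises only if an inpatient urine result is missing and urine PK was still reported. Neither can be determined here, so confidence is medium. The falls in the mean depend only on the number of active subjects; the CV figures and the chances of a missing result also rest on the assumed values above.

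The Day -1 collection is a separate matter. It precedes dosing and is expected to be 0, so its geometric summary is blocked in any case.

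**What to change.** Replace the exception in SAP 7.3(2) with:

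> If urine volume or concentration is missing for a collection interval, Ae, Ae% and any parameter derived from them (including CLR) are missing for that interval. Zero is used only for a measured BLQ concentration or a documented zero volume.

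This removes the conflict with the preceding sentence and brings urine into line with the plasma handling. The cost is one SAP sentence. A subject with a missing result drops out of that day's urine summary, which reduces n by 1 in an already small group.

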## 7.4 Handling of data for PK assessments

PK data that are considered "invalid" will be flagged in the listing. The PK data handling was assessed during BDRM prior to database lock and in the investigation of PK data handling assessment after unblinding. A separate PK data handling document will be produced to cover both pre- and post- unblinding decisions.

If PK sample handling errors or other factors are identified after data unblinding and these errors have led to unexpected erroneous data, then these erroneous data will be regarded as "invalid".

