**7.4 Maintenance of the study blind and unblinding**

This is a double-blind study. Treatment assignment will not be known to the subjects, the Sponsor or the staff who are involved in the clinical evaluation of the subjects and the analysis of data. The randomisation schedule and disclosure envelopes will be generated by an unblinded statistician at

STUDY PROTOCOL

[REDACTED] according to [REDACTED] SOPs. The unblinded statistician will not be involved in any decisions relating to populations for analysis prior to unblinding.

For each subject, sealed treatment decode envelopes will be held in a secure area by the Investigator and Sponsor. The sealed code should not normally be broken for reasons other than safety or in an emergency. Should the Investigator wish to break the code for such reasons, he/she should ideally consult the Sponsor in advance. If this is not possible, the Investigator may break the code and document the date and reason for breaking the blind without prior discussion with the Sponsor. The Sponsor should be notified as soon as possible thereafter. If the blind is broken for any individual subject, the subject must be withdrawn from the study, and any procedures accompanying withdrawal should be performed (Section 4.5).

If the study stopping criteria appear to be met, the Sponsor will unblind individual subject allocations to confirm stopping criteria have been met. The specific mechanism for unblinding will be outlined in a separate document.

The Sponsor will authorise release of the unblinded randomisation list at the end of the study.

Prior to database lock and unblinding, all original randomisation materials, including the original final signed and dated randomisation schedule, will be held by the Quality Assurance (QA) department at [REDACTED]. The Data Sciences department will not have access to the randomisation schedule before database lock and unblinding.

A copy of the final randomisation schedule will also be made available to MTPE Clinical Supplies and the laboratory performing the bioanalysis to allow selective analysis of drug concentrations. The blind of the study will be broken after the study database has been locked and the safety population has been defined for that part. Any request for issue of the randomisation schedules must be made using a randomisation disclosure form.

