#### 4. PLANNED ANALYSIS

This SAP will be finalized before database lock. Final data analysis will be conducted after database lock.

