#### 5. ANALYSIS POPULATIONS

Analysis Population	Definition
Randomised Population (RAND)	All subjects randomised.
Safety analysis set (SAF)	All randomized subjects who received at least one dose of IMP.
PK analysis set (PKPOP)	All subjects who complete the study without having a major emesis episode within 2 hours of dosing on that day and have evaluable PK parameters. The PK data from subjects with emesis within 2 hours of dosing may be analysed separately.

The SAF or RAND will be used for study population-related evaluations. The SAF will be used for all safety evaluations. The PKPOP will be used for the PK analyses.

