### **7.1.3. Pharmacokinetics Evaluation**

#### **7.1.3.1. Plasma Concentration**

For the calculation of the summary statistics, concentration values reported as below the limit of quantification (BLQ) will be set to 0. Only valid PK data will be included in the summary tables or figures.

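### SAP 7.4 lets PK data be ruled invalid after unblinding on an undefined ground, needs no evidence apart from the concentration, and does not require the effect of the exclusion to be shown

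*SAP*

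**What the plan says.** SAP 7.4 describes two rounds of PK data handling: one at the blinded data review meeting before lock, and one "in the investigation of PK data handling assessment after unblinding". On the later round it says: "If PK sample handling errors or other factors are identified after data unblinding and these errors have led to unexpected erroneous data", the data count as invalid. Invalid data are flagged in the listing. The decisions are to be recorded: "A separate PK data handling document will be produced to cover both pre- and post- unblinding decisions".

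The consequence is in SAP 7.1.3.1: "Only valid PK data will be included in the summary tables or figures".

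Protocol 7.4 has the blind broken "after the study database has been locked and the safety population has been defined for that part". It does not mention the PK analysis set. SAP 5 makes membership of that set depend, among other things, on subjects who "have evaluable PK parameters", without saying what makes a parameter evaluable.

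The result most exposed is in SAP 8.3.3. Single-dose AUC and Cmax are regressed on dose on the log scale, and proportionality is concluded if the 95% CI for the slope contains 1.

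**The concern.** An exclusion rule protects against bias if it is fixed before the results are known, or if it rests on facts that do not depend on the result. The late rule in SAP 7.4 secures neither. A value that stands out once treatment is known can start a search for a cause, and the open second ground sets no standard for what counts as one. Values that look ordinary are not searched in the same way.

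Cohorts are small, so one subject carries weight in the geometric mean, in the geometric CV% (SAP 6.1) and in the slope. The plan does not call for these results to be shown both ways, so the effect of an exclusion would not appear in the tables.

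**Working it through.** **Text check**

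1. *Conditions for late invalidation.* SAP 7.4 asks for an identified error or factor, that it led to the data, and that the data are erroneous. Handling errors are a recognisable class. Other factors are not defined, nor is the standard for erroneous. No source record, blinded assessor or second analysis is required.
2. *Consequence.* The data leave summary tables and figures (SAP 7.1.3.1) but stay in the listings with a flag (SAP 7.4, 8.3.1).
3. *Timing.* Protocol 7.4 names two conditions for breaking the blind: database lock and the safety population. The blinded review assesses PK handling before lock, but its decisions are not stated to be final, and the handling document expressly covers later ones.

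**Size of a worst-case exclusion**

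The documents give no variability and no figure to reproduce, so CVs of 30%, 40% and 50% are assumed. Planned active numbers are 6 per Part 1 cohort (Protocol 3.1). The log-scale SD is σ = √ln(1 + CV²), which gives 0.294, 0.385 and 0.472.

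In 400,000 simulated cohorts of 6 log-normal values, with no drug anomaly and no error, the subject furthest from the cohort mean was dropped:

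- Mean absolute shift of the log mean: 0.294σ. Factor on the geometric mean, exp(0.294σ): exp(0.086) = 1.09, exp(0.113) = 1.12, exp(0.139) = 1.15.
- Ratio of SD after to SD before: 0.708, a cut of 29%. At CV 40%, 0.708 × 0.385 = 0.273, and √(exp(0.273²) − 1) = 0.28, so 40% would read about 28%.

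SAP 3.3.2 gives 44 subjects in Part 1. With six cohorts of 8 or 6, this means four of 8 and two of 6 (4 × 8 + 2 × 6 = 44). The active split of the smaller cohorts is not stated. If 4 were active, the shift is about 0.40σ (12%, 17% and 21%) and the SD ratio about 0.57.

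For comparison, dropping one of 6 at random shifts the log mean by 0.146σ on average, with an SD ratio of 0.99. At CV 40% that is exp(0.146 × 0.385) = 1.06.

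**Slope**

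The doses are redacted. Assume active numbers of 6, 6, 6, 6, 4, 4 and dose steps of either 5, 4, 3, 3, 3-fold (the protocol's maximum factors) or 3, 2, 2, 2, 2-fold.

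- Dropping the most extreme subject from one randomly chosen cohort at CV 40% moves the slope by about 0.008 to 0.013, against a 95% CI half-width of about 0.07 to 0.11.
- If the subject is instead picked to change the conclusion, one removal reversed whether the CI contains 1 in about 8% to 36% of simulated trials (CV 30% or 50%, true slope 1.00, 0.95 or 0.90, 1,000 trials per scenario).

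The first figure is an unselective removal. The second is the upper limit of what deliberate selection of one subject could do.

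**The case against.** Several stronger readings are tempting, and the documents do not support them.

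- *That a value can be excluded simply because it looks unexpected.* SAP 7.4 asks for an identified error or factor that produced erroneous data. Being unexpected narrows the rule and is not sufficient alone. What stands is that nothing prevents the look of the value from prompting the search, and the second ground is open.
- *That a reader could not see what was done.* Flags, full listings, a listing of analysis-set membership (SAP 8.1.2) and a decision document are all planned. What is missing is the effect on the summaries and the slope.
- *That the PK set is left open until after unblinding.* The documents do not say so; they are silent on when it is final, and a pre-lock review exists. The past tense in SAP 7.4, beside "This SAP will be finalized before database lock" in SAP 4, does not show otherwise: this SAP was written after termination and mixes tenses throughout.
- *That 9% to 15% is the expected effect.* It describes loss of the most extreme whole subject. A single-dose profile has 18 PK samples (Protocol Table 6), and SAP 7.1.3.2 calculates AUC as if a missing sample had never been scheduled. If invalid samples are treated the same way, losing one leaves the subject in.
- *That exclusions would move the slope toward proportionality.* The direction is not established.

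The stakes are also limited. PK is secondary, no statistical tests apply (SAP 6.2), Protocol 10.3.5.4 describes dose proportionality as exploratory, the mixed model was not done (SAP 10), and the primary safety analysis uses the safety set. All of this stands and lowers the weight of the point. It does not supply the missing criterion.

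**Conclusion.** The point holds in a limited form. SAP 7.4 is a stated permission to exclude PK data after unblinding on a ground with no criterion, without evidence independent of the value and without showing the effect. Exclusions can therefore be prompted by the result. The documents give no sign that any were.

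The worst-case size is a shift of about 9% to 15% in a cohort geometric mean and a 29% smaller log SD, for loss of the most extreme whole subject out of 6 at an assumed CV of 30% to 50%. It is larger if a cohort had 4 active subjects, and usually much smaller for a single sample. The results at risk are the PK summaries and the Part 1 dose-proportionality conclusion, not the primary safety results. This is a cheap improvement rather than a flaw that undermines the study.

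**What to change.** - In SAP 7.4, replace the other-factors ground with a requirement that any exclusion after unblinding rests on an error documented in source, handling or bioanalytical records, independently of the concentration value.
- Record the PK set and all known exclusions at the blinded review, before the code is broken. This is a partial safeguard only: dose is known by cohort, only samples from active subjects are assayed (Protocol 6.4), and interim PK is reviewed under alias numbers during escalation (Protocol 3.4). Freezing the set would not make later decisions blind to results.
- For any value excluded after unblinding, present the affected PK summaries and the slope with its 95% CI, with and without it. If lock has passed, this can go in the clinical study report.

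The cost is a few sentences of SAP text and, if any value is affected, a few repeated PK tables. The drawback is that a suspect value with no documented cause stays in the main summary. Genuine handling errors found late can still be excluded.
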